1.0 BACKGROUND AND HYPOTHESES

- 1.1 The prevalence of alcohol-associated liver disease (ALD) has been increasing due to ongoing alcohol use and high-risk drinking over the past decade¹. ALD now poses a significant burden to the US healthcare system, accounting for 5.4 per 100,00 deaths in 2012, and ALD mortality is increasing particularly in younger demographics². Given the increased prevalence of ALD in conjunction with a 5-fold increase in liver transplant (LT) for severe alcohol associated hepatitis (AH)³, ALD is now the leading indication for liver transplantation accounting for approximately 30% of LT waitlist additions and 24% of LT recipients in 2016 in the US1. Despite excellent surgical outcomes, ~50% liver graft recipients with alcohol use disorder (AUD) relapse (any alcohol use) by 5 years post- (LT)⁴. Those post-LT patients that go on to develop harmful drinking patterns (early onset, moderate to heavy alcohol use) have increased rates of graft failure highlighting a population that would likely benefit from comprehensive treatment of AUD, including pharmacotherapy⁵. Though not contraindicated, to date, no AUD medication has been FDA-approved for use in patients with ALD⁶. Naltrexone and disulfuram are both FDA approved but have a black box warning for hepatoxicity⁶. Although, small studies have shown the benefit of pharmacotherapy in patients with ALD, no studies have been done to validate the use of AUD pharmaceuticals in the post-LT population⁷. Due to combination of factorsprovider discomfort, lack of data regarding pharmaceutical effectiveness and safety in this population, and lack of treatment protocols to treat AUD in this specific population, our post-LT population has not received standard of care for AUD⁷. Failure to utilize available and effective interventions predisposes this patient population to alcohol relapse (e.g. slips), subsequent harmful drinking patterns (early onset, moderate to heavy alcohol use), and ultimately graft dysfunction⁵.
- 1.2 Acamprosate is an effective FDA approved adjunct therapy for alcohol dependence in adults⁸. However, there is limited literature on the use of acamprosate in patients with ALD, and there is no literature on the use of acamprosate in post-LT ALD patients^{7,8}. It is well established that acamprosate is not metabolized by the liver and unlikely to interfere with medications metabolized via cytochrome P450⁸. Given this unique pharmacokinetic property of acamprosate, there should be no drug-drug interactions with its use in LT recipients⁹.
- 1.3 We hypothesize that acamprosate will be a feasible AUD therapy for post-LT patients.

2.0 OBJECTIVES AND PURPOSE

Keck Medicine of USC's Liver Transplant Program will develop a pilot study to incorporate acamprosate use in suitable post-LT individuals. A research team will provide weekly appointments to administer surveys to assess for alcohol use, alcohol cravings, acamprosate compliance, and drug side-effects. Patients will obtain laboratory values and visit their transplant hepatologist monthly as is standard of care. Patients will also receive a consultation with the program's transplant pharmacist to reconcile medications to avoid drug-drug interactions.

The primary goals of this study are:

- 2.1 To evaluate the feasibility and safety of acamprosate for management of AUD in post-liver transplant patients
- 2.2 To determine whether acamprosate use in combination with standard of care (weekly telephone visit) reduces the frequency of alcohol relapse


4.0 DRUG/DEVICE INFORMATION

- 4.1 Acamprosate is the drug that will be utilized in the proposed study. This is an FDA approved commercially available drug for alcohol dependence and abuse in the United States since 2004. Acamprosate is available in delayed release tablets of 333 mg generically and under the brand name campral. The typical maintenance dose is 666 mg three times daily.
- 4.2 Acamprosate will be the only drug being utilized in this study.
- 4.3 IND/IDE number not applicable.
- 4.4 Acamprosate will be prescribed and sent to patients preferred pharmacy.
- 4.5 Acamprosate (a kam' proe sate) is N-acetylhomotaurine, a synthetic amino acid analogue similar to gamma aminobutyric acid (GABA) and taurine that has been shown to decrease alcohol craving in

animal models. Acamprosate appears to function as a neurotransmitter with GABA agonist and partial glutamate (N-methyl-D-aspartate [NMDA]) antagonist activity, but its precise mechanism of action in decreasing alcohol craving is unknown¹⁰. Acamprosate appears safe and well-tolerated for the maintenance of abstinence in alcohol-dependent patients across a wide range of patient groups⁸. Flatulence is the only other adverse effect that has been significantly associated with acamprosate over placebo¹¹ with no statistically significant differences were observed between groups (acamprosate versus placebo) of premature withdrawals from treatment due to adverse effects¹².

Acamprosate has a low propensity for interactions with other drugs⁸. Acamprosate is contraindicated in patients with hypersensitivity to acamprosate calcium or any of its components and patients with severe renal impairment (CrCl of 30 mL/min or less) as Acamprosate is primarily renally excreted¹³. There were no sex differences in safety or tolerability for acamprosate⁸. Acamprosate appears generally safe in patients with impaired hepatic function⁸.

5.0 SELECTION AND WITHDRAWAL OF SUBJECTS

Beginning January 1st, 2022, we will recruit patients from Liver Transplant Program from the USC Transplant Institute's patient census. We will target at least 25-30 patients for this study with 2:1 randomization (acamprosate plus SOC vs SOC alone). All patients must have history of LT with a pre-LT diagnosis of ALD. As our usual number of transplants per year is 120 and 30% of patients have ALD (includes AH) as a diagnosis, we do not anticipate any difficulties in identifying 30 participants for this study.

Enrollment will be on a rolling basis.

- 5.1 Patients must have received a transplant for liver disease secondary to alcohol-associated hepatitis or alcohol-associated cirrhosis.
- 5.2 We will exclude patients with hypersensitivity to acamprosate calcium or any of its components, severe renal impairment (creatinine clearance ≤30 mL/min), psychopathology under treatment with psychoactive drug, substance dependence other than THC, alcohol, or nicotine, need for inpatient detoxification or inpatient treatment of alcohol use, participation in a clinical trial within the past 30 days, and women of childbearing potential who do not practice a medically acceptable form of contraception will be excluded.

We will obtain an informed consent for all patients. As part of the informed consent, participants will be expected to complete a weekly telemedicine visit with a research member for at least 3 months, required to fill out weekly surveys (Appendix III) (Penn Alcohol Craving Scale (PACS), Alcohol Timeline Followback (TLFB), and Generic Assessment of Side Effects in Clinical Trials (GASE) prior to these visits and expected to be compliant with acamprosate if randomized to that group. The proportion of patients eligible but who did not agree to participate will be captured.

5.3 Patients may withdraw from study at any time. If patients suffer any severe adverse effects from acamprosate they will be advised to stop the drug immediately and withdraw from the study.

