parameter measured: including mean values for the liver function tests aspartate aminotransferase (AST), alanine aminotransferase (ALT) and gamma-glutamyl transferase (GGT)¹¹. Acamprosate therapy has not been associated with serum enzyme elevations over and above rates that occur with placebo therapy. Despite wide-scale use in alcohol treatment programs, there have yet to be published reports of clinically apparent acute liver injury attributed to acamprosate therapy¹⁰. Pharmacovigilance data in 1.5 million patients has indicated no serious adverse events⁸.

Acamprosate's package insert includes a precaution for suicidality due to an increase in adverse events of a suicidal nature (suicidal ideation, suicide attempts, completed suicides) in acamprosate treated patients. The insert recognizes the complex and well-recognized interrelationship between alcohol dependence, depression and suicidality and encourages that "all alcohol-dependent patients, including those patients being treated with CAMPRAL should be monitored for the development of symptoms of depression or suicidal thinking." There is no evidence of a statistically significant association between treatment with acamprosate and adverse events of a suicidal nature^{8,14,11,12}. Acamprosate has a low propensity for interactions with other drugs, including those likely to be administered as concomitant drugs in alcoholdependent patients, including alcohol, diazepam, disulfiram or naltrexone. In vitro studies indicate that acamprosate does not induce cytochrome P450 (CYP) 1A2 or 3A4 isoenzymes, nor does it inhibit the metabolism of drugs that are substrates for CYP1A2, 2C9, 2C19, 2D6, 2E1 or 3A4¹⁶. Micromedex has no reported drug interactions with acamprosate¹³. However, coadministration of naltrexone with acamprosate significantly increased the maximum plasma concentration and the area under the plasma concentration-time curve of acamprosate 14,17. No adverse effects were documented¹⁷. No adjustment of dosages is recommended in patients with co-administration of naltrexone with acamprosate¹⁴.

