9.0 CLINICAL AND LABORATORY EVALUATIONS AND STUDY CALENDAR

Parameter	Pre-	Day 1	Weekly	Bi-monthly
	Treatment			
Targeted History (alcohol history, psychiatric history, liver transplant history, medications history, social history, abdominal imaging, pregnancy test if indicated)	X			
Complete Blood Count (CBC)	X			X
Complete Metabolic panel (CMP)	X			Χ
Alcohol Metabolites	Х	-		X

Immunosuppression levels	X			Х
Penn Alcohol Craving Scale (PACS)	X		X	
Quick Drinking Screen	X		X	
Timeline Follow back	X		X	
General Assessment of Side Effects in			Х	
Clinical Trials (GASE)				
Agent administration		X^1		
Interval history (hospitalizations,			X	
medication changes)				

¹daily

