Irritability, nervousness	○ 0 ○ 1 ○ 2 ○ 3 (Intensity)
Is this complaint related to your current medication?	○ Yes ○ No
Depressed mood	○ 0 ○ 1 ○ 2 ○ 3 (Intensity)
Is this complaint related to your current medication?	○ Yes ○ No
Thoughts about suicide	○ 0 ○ 1 ○ 2 ○ 3 (Intensity)
Is this complaint related to your current medication?	○ Yes ○ No
Anxiety, Fearfulness	○ 0 ○ 1 ○ 2 ○ 3 (Intensity)
Is this complaint related to your current medication?	○ Yes ○ No

- 0 = Complaint not present
- 1 = Mild: complaint causes mild distress or discomfort, but no impairment in daily functioning
- 2 = Moderate: complaint causes moderate distress or discomfort or at least some impairment in daily

functioning

3 = Severe: complaint causes severe distress and discomfort, severe impairment in daily functioning,

or acute danger to health

Have you had any further symptoms?	○ Yes ○ No (Please name the symptom)	
How many additional symptoms have you had?	○ 1 ○ 2 ○ 3 ○ 4 (Intensity)	
What was the first symptom?		
	(Please name the symptom)	
What was the intensity of the first symptom? ([symptom1])	○ 0 ○ 1 ○ 2 ○ 3 (Intensity)	
Is this complaint related to your current medication?	○ Yes ○ No	
What was the second symptom?		
	(Please name the symptom)	
What was the intensity of the second symptom? ([symptom2])	○ 0 ○ 1 ○ 2 ○ 3 (Intensity)	
Is this complaint related to your current medication?	○ Yes ○ No	
What was the third symptom?		
	(Please name the symptom)	
What was the intensity of the third symptom? ([symptom3])	\bigcirc 0 \bigcirc 1 \bigcirc 2 \bigcirc 3 (Intensity)	
Is this complaint related to your current medication?	○ Yes ○ No	
Please list the additional symptom(s) you are		
experiencing and relay them to your study coordinator at the next study appointment	(Please name the symptom(s))	

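### Untreated depression and current suicidal thoughts meet no exclusion in section 5.2, and with no pre-treatment GASE reading, symptoms already present count as on-study side effects

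*Combined protocol and SAP*

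**What the plan says.** **Entry.** Section 5.2 contains one psychiatric exclusion, "psychopathology under treatment with psychoactive drug". The other exclusions cover hypersensitivity, renal function, dependence on other substances, contraception, and "need for inpatient detoxification or inpatient treatment of alcohol use, participation in a clinical trial within the past 30 days". None concerns mental state.

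**Risk named.** Section 8.1 reports that the package insert carries a "precaution for suicidality due to an increase in adverse events of a suicidal nature" and quotes its advice that alcohol-dependent patients "should be monitored for the development of symptoms of depression or suicidal thinking". It then adds: "There is no evidence of a statistically significant association between treatment with acamprosate and adverse events of a suicidal nature".

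**Assessment.** In the section 9.0 calendar the first row, "Targeted History (alcohol history, psychiatric history, liver transplant history" and further items, is marked pre-treatment. The row beginning "General Assessment of Side Effects in" is marked in the weekly column only. PACS and the Timeline Followback are marked both pre-treatment and weekly. Section 3 agrees: it names baseline drinking and baseline craving but no baseline GASE, and has the acamprosate group start the drug after the initial visit. The GASE form in the appendix has a depressed-mood item and an item "Thoughts about suicide", each scored 0 to 3 over the preceding seven days.

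**Endpoint.** Sections 10.0 and 13.1 define safety as the percentages of GASE side effects, in total and by severity, and compare them with the control group. Section 10.0 adds mortality. Neither section mentions a baseline value.

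**The concern.** The psychiatric criterion turns on whether the condition is being treated with a drug, not on the patient's present state. Read literally, a stable patient on an antidepressant is excluded, while a patient with untreated depression or current suicidal thoughts is not. That may be intended, for instance to keep psychoactive drugs out of the comparison, but the protocol does not say so. Psychiatric history is taken before treatment, yet no rule uses it for untreated illness.

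The statistical consequence lies in the safety endpoint. Watching for the development of a symptom requires knowing whether it was there at the start. Without a pre-treatment reading, a complaint that predates randomisation is counted as a side effect on study. Safety is half of goal 2.1, the arms are small, and the treatment is open, so nothing else in the design separates the two kinds of report.

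**Working it through.** The documents give no figure to reproduce. The check is a reading of the text, followed by an illustration of scale.

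**1. Can such a patient enter?** Going through 5.2 item by item, a patient with untreated depression or current suicidal thoughts meets none of the exclusions. Sections 3, 6 and 14 add no psychiatric criterion. The gap is confirmed.

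**2. Is there a pre-treatment value?** The calendar marks compare as follows.

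| Instrument | Pre-treatment | Weekly |
|---|---|---|
| PACS | yes | yes |
| Timeline Followback | yes | yes |
| GASE | no | yes |

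The first GASE form looks back seven days. Because the drug starts after the initial visit, a form completed at the first weekly contact would already cover time on treatment.

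**3. Does the endpoint remove pre-existing symptoms?** No. Sections 10.0 and 13.1 use the survey percentages as they stand. Each GASE item also asks whether the complaint is related to current medication. That does not solve the problem: the endpoint is not limited to related complaints, the question is not specific to acamprosate, and the patient answers it knowing the arm.

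**4. Scale, as illustration.** Inputs: 30 patients (upper end of the target in 5.0) at 2:1, hence 20 v 10. The number k who enter with such symptoms is not in the documents and is assumed. Each is taken to report the symptom on study, and the drug to have no effect. Ignoring stratification by sex, the chance that j of the k fall in the acamprosate arm is C(20, j) × C(10, k − j) / C(30, k). For k = 3 the denominator is C(30,3) = 4060.

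| Split (acamprosate v SOC) | Count | Probability | Observed rates |
|---|---|---|---|
| 3 v 0 | 1140 | 28% | 15% v 0% |
| 2 v 1 | 190 × 10 = 1900 | 47% | 10% v 10% |
| 1 v 2 | 20 × 45 = 900 | 22% | 5% v 20% |
| 0 v 3 | 120 | 3% | 0% v 30% |

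The four counts sum to 4060. The acamprosate rate is higher in 28% of allocations and the SOC rate in 22% + 3% = 25%. The expected rates are equal: 3 × 20/30 = 2 of 20, and 3 × 10/30 = 1 of 10, both 10%.

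Range: with k = 2, all fall on acamprosate with probability 190/435 = 44% and all on SOC with 45/435 = 10%. With k = 5 the figures are 15504/142506 = 11% and 252/142506 = 0.2%.

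Pre-existing symptoms therefore do not bias the difference in one direction. They raise the apparent rate in both arms and add chance imbalance that cannot be recognised afterwards.

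**The case against.** A reader might infer that 5.2 contradicts the precaution in 8.1. It does not. The quoted advice asks for monitoring, not exclusion, and weekly GASE in both arms, with items on both symptoms, partly provides it. Section 3 sends new symptoms to the transplant hepatologist, and 7.32 allows treatment to be held or stopped for moderate to severe effects. Section 8.1 also reports no statistically significant association. What remains is that monitoring for development lacks a starting point.

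A reader might also infer that the patients at highest risk are being let in. Nothing in the documents ranks untreated patients above drug-treated ones for suicidal events.

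Nor do a few such patients settle the safety result. GASE lists about 36 complaints, and two of them do not determine a total percentage. Even the extreme split, 3 of 20 v 0 of 10, has a two-sided Fisher p of 0.53: the splits no more likely than the observed one sum to (1140 + 900 + 120)/4060. The gap between 28% and 3% reflects the 2:1 ratio and would appear for any baseline trait.

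Finally, whom to exclude on psychiatric grounds is a clinical decision with a recruitment cost. Section 5.0 implies about 120 × 30% = 36 transplants for alcohol-associated disease a year, for a target of 25 to 30 patients. This objection stands, and it is why the remedy below rests on measurement and not on a new exclusion.

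**Conclusion.** The concern holds in limited form. Section 5.2 leaves untreated depression and current suicidal thoughts outside any exclusion without stating the purpose of its drug-treatment criterion. Section 9.0 gives GASE no pre-treatment reading, so the safety percentages mix symptoms that were present before treatment with symptoms that developed on study. Both facts come directly from the text and rest on no assumption.

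The size is uncertain, because the number of such patients is unknown. The 28%, 47% and 3% for an assumed three patients show what chance alone can do with 20 v 10; they are not a forecast. The documents support neither a conflict with the quoted precaution nor a systematic bias against acamprosate. This is a cheap improvement to the safety comparison, not a defect that invalidates it.

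**What to change.** **Baseline reading.** In section 9.0 add a pre-treatment mark for GASE, and in section 3 list it with baseline TLFB and PACS, to be completed before randomisation in both arms. At a minimum, record the depressed-mood and suicidal-thoughts items.

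**Endpoint.** In sections 10.0 and 13.1, report on-study GASE events as new or worsened, meaning an intensity above the patient's own baseline score, by arm with denominators. Show psychiatric history by arm beside them. A single baseline week is set against up to 14 weekly forms, so fluctuating complaints will sometimes count as worsened. That applies to both arms on the same schedule and should be stated.

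**Reconciliation.** The sponsor and investigators should reconcile 5.2 with 8.1, state what the drug-treatment criterion is for, and decide whether current psychiatric state should bear on eligibility. That decision and any threshold are theirs.

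**Cost.** One extra completion of an existing form per patient, and a few lines of text. The baseline reading itself excludes no one.

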6.0 STRATIFICATION/DESCRIPTIVE FACTORS/RANDOMIZATION SCHEME

- 6.1 Sex will be balanced across treatment arms due to the pilot nature of this study, age, race ethnicity and time from transplant will be recorded for planning of future trials.
- 6.2 Drinking history, social history, pre-liver transplant relapse probability scores, medical history, and medication history will be obtained.
- 6.3 Randomization will occur via an unblinded 2:1 ratio of acamprosate plus SOC versus SOC alone respectively stratified by sex.

7.0 STUDY AGENT ADMINISTRATION OR INTERVENTION AND TOXICITY MANAGEMENT PLAN

7.1 Treatments

A. Standard of Care (SOC): Participants will be expected to complete a weekly telemedicine visit with a research member for at least 3 months, required to fill out weekly surveys (figure 2) (Penn Alcohol Craving Scale (PACS), Alcohol Timeline Followback (TLFB), and Generic Assessment of Side Effects in Clinical Trials (GASE) prior to these visits and expected to be compliant with acamprosate if randomized to that group.

B. SOC+ Acamprosate: Participants randomized to this arm will participate in SOC + take acamprosate 666 mg TID daily for three months.

7.21

AGENT	DOSE	ROUTE	DAYS	ReRx INTERVAL	NOTES
Acamprosate	666 mg	PO TID	Daily	4 weeks	maximum cumulative dose 500 mg/m ²

- 7.31 A patient may always be removed from treatment whenever he/she wishes
- 7.32 Treatment will be discontinued or held at discretion of investigators if patients experience any moderate-severe side effects as evaluated in section 8.0 thought to be secondary to acamprosate.

8.0 ASSESSMENT OF EFFICACY AND SAFETY

8.1 Acamprosate's package insert includes a comprehensive list of adverse events in over 7000 patients exposed to acamprosate¹⁴. However, adverse events are listed without regard to the causal relationship of the events to the drug¹⁴. Only diarrhea and flatulence appear to be significantly associated with acamprosate¹⁴. There is no evidence that acamprosate has additional risks in the liver transplant population⁸. Multiple meta analyses have found that the only side effect significantly associated with acamprosate over placebo is diarrhea^{8,15}. Flatulence is the only other adverse effect that has been significantly associated with acamprosate over placebo¹¹. In a review of clinical trials, diarrhea was observed in 10-17% of patients treated with acamprosate (versus 10-11% in placebo)^{11,12}. Diarrhea appears to be acamprosate dose dependent, settles within a few days, and mostly mild or moderate in severity¹¹. If diarrhea was severe, temporary dose reduction was beneficial⁸. Of note, no statistically significant differences were observed between groups (acamprosate versus placebo) in terms of premature withdrawals from treatment due to adverse effects¹². No clinically meaningful differences have been found comparing acamprosate and placebo regarding the incidence of clinically significant postbaseline abnormalities for any hematology

parameter measured: including mean values for the liver function tests aspartate aminotransferase (AST), alanine aminotransferase (ALT) and gamma-glutamyl transferase (GGT)¹¹. Acamprosate therapy has not been associated with serum enzyme elevations over and above rates that occur with placebo therapy. Despite wide-scale use in alcohol treatment programs, there have yet to be published reports of clinically apparent acute liver injury attributed to acamprosate therapy¹⁰. Pharmacovigilance data in 1.5 million patients has indicated no serious adverse events⁸.

Acamprosate's package insert includes a precaution for suicidality due to an increase in adverse events of a suicidal nature (suicidal ideation, suicide attempts, completed suicides) in acamprosate treated patients. The insert recognizes the complex and well-recognized interrelationship between alcohol dependence, depression and suicidality and encourages that "all alcohol-dependent patients, including those patients being treated with CAMPRAL should be monitored for the development of symptoms of depression or suicidal thinking." There is no evidence of a statistically significant association between treatment with acamprosate and adverse events of a suicidal nature^{8,14,11,12}. Acamprosate has a low propensity for interactions with other drugs, including those likely to be administered as concomitant drugs in alcoholdependent patients, including alcohol, diazepam, disulfiram or naltrexone. In vitro studies indicate that acamprosate does not induce cytochrome P450 (CYP) 1A2 or 3A4 isoenzymes, nor does it inhibit the metabolism of drugs that are substrates for CYP1A2, 2C9, 2C19, 2D6, 2E1 or 3A4¹⁶. Micromedex has no reported drug interactions with acamprosate¹³. However, coadministration of naltrexone with acamprosate significantly increased the maximum plasma concentration and the area under the plasma concentration-time curve of acamprosate 14,17. No adverse effects were documented¹⁷. No adjustment of dosages is recommended in patients with co-administration of naltrexone with acamprosate¹⁴.

Acamprosate is contraindicated in patients with hypersensitivity to acamprosate calcium or any of its components and patients with severe renal impairment (CrCl of 30 mL/min or less)¹³. Acamprosate is primarily renally excreted. Peak plasma concentrations after administration of a single dose of 2 x 333 mg Acamprosate tablets to patients with moderate or severe renal impairment were about 2-fold and 4-fold higher, respectively, compared to healthy subjects¹³. Acamprosate is known to be substantially excreted by the kidney, and the risk of toxic reactions to this drug may be greater in patients with impaired renal function¹³. There were no sex differences in safety or tolerability for acamprosate⁸. Acamprosate appears generally safe in patients with impaired hepatic function⁸. There is no evidence, clinical or theoretical, that Acamprosate is not safe in the liver transplant population. Acamprosate may improve morbidity and mortality in liver transplant patients by mitigating the risks associated with continued alcohol use.

The greatest proportion of deaths or re-transplants after liver transplantation occur soon after initial transplantation. The causes of death and graft loss vary according to the interval from transplantation, with infection and intraoperative and perioperative causes accounting for nearly 60% of deaths and graft losses in the first posttransplant year. After the first year, death due to acute infections declines, whereas malignancies and cardiovascular causes account for a greater proportion of deaths. The recurrence of the pretransplant condition, especially hepatitis C virus (HCV) or autoimmune liver disease, is an increasingly important cause of graft loss the longer the patient

survives transplantation for these etiologies [10]. There is no evidence, clinical or theoretical, of a link between acamprosate and any of the above causes of morbidity and mortality in liver transplant patients in the first-year post-transplant^{8,15,11,12}.

Though no causal relationships to acamprosate have been found, the adverse of acute kidney failure has been reported to be temporally associated with acamprosate in several patient¹³. There is no evidence of a link between acamprosate and any of the other above causes of morbidity and mortality in liver transplant patients following the first-year post-transplant^{8,15,11,12}.

- 8.11 Patients will undergo a self-administered weekly survey, Generic Assessment of Side Effects in Clinical Trials (GASE) to evaluate for potential side effects and toxicities. They will also undergo standard of care laboratory testing as well to check renal function and graft function along with immunosuppression levels. Details regarding the survey are listed in Appendix III.
- 8.12 There are no known long term drug toxicities associated with acamprosate. The recommended long-term dose for acamprosate is 666 mg TID PO daily unless the patient has severe renal impairment (CrCl of 30 mL/min or less) or levels hypersensitivity to acamprosate calcium or any of its components, in which case, acamprosate is contraindicated. If the patients choose to continue acamprosate after this study, they will continue to follow with their primary transplant hepatologist who can monitor for adverse side effects such as kidney dysfunction, hypersensitivity, diarrhea, and flatulence.
- 8.2 Complete discontinuation is advised if the patient experiences any drug toxicities related to acamprosate. Patients should not restart treatment if toxicity is thought to be related to acamprosate.
- 8.3
- 8.31 If a patient experiences an adverse event such as an unexpected or fatal toxicity, the event will be immediately (within 24 hours) reported to the primary medical care team so patient can receive the appropriate care.
- 8.32 We will then report the event to the IRB and FDA.

